Surprisingly, mild psoriasis was characterized by significantly higher IL-17A expression, stronger expression of the core psoriasis transcriptome, and by higher numbers of T-cells in skin lesions. In contrast, severe psoriasis was characterized by stronger expression of some epidermal response genes (TGFA, CALM1, SMPD3 & IL1RL2). However, a key molecular distinction between mild and severe psoriasis was higher expression of negative immune regulatory genes (CTLA4, PD-L1 & CD69) in mild lesions compared to severe psoriasis lesions.

These data have relevant implications for therapy of psoriasis—first they suggest that anti-IL-17A approaches used in severe psoriasis might be equally (or even more) effective in mild psoriasis. Secondly, restoration of immune tolerance might be more easily achieved in mild psoriasis due to higher “regulatory” immune tone that effectively prevents unbounded T-cell expansion. Thus, short-term anti-IL-17A treatment of mild psoriasis might prevent the recurrence and eventually cure psoriasis. The aim of the study is to test this hypothesis by exploring whether 3 months or 6 months of Secukinumab treatment will prevent relapses after medication has been discontinued in mild psoriasis patients.

12.4 * Engaging Stakeholders: Describe any plans to engage other stakeholders (Scientists, practitioners, patients, advocacy groups, etc.) for hypothesis generation, or feasibility purposes.

We will engage stakeholders, including participants, their families, their health care providers, and the study sponsor, and to assure safe progression of the study and to address any concerns may arise.

12.5 * Hypothesis

Describe the *research hypothesis* in a single sentence.

COSENTYX (secukinumab) is efficacious in treating mild, chronic plaque type of psoriasis in adults.

12.6 * Aim(s)

Indicate how you will *address the hypothesis* (e.g., to compare groups, to estimate a parameter, to ascertain feasibility). Since the sample size determination is usually based on the primary aim only, the primary aim should be sufficient to justify the study.

- 1) To evaluate the efficacy of secukinumab for the complete resolution of mild plaque-type psoriasis after 3 months of secukinumab treatment by comparing the secukinumab-receiving mild psoriasis subjects (Group 1) and the placebo-receiving mild psoriasis subjects (Group 2).

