*Mild psoriasis - psoriasis affected Body Surface Area (BSA) less than 10% and Psoriasis Area and Severity Index (PASI) between 6 and 12.
*Group 1 : 6 months secukinumab + 12 months observation
*Group 2 : 3 months placebo + 3 months secukinumab + 12 months observation
- 2) To explore whether secukinumab will prevent relapses after medication has been discontinued in subjects with mild plaque-type psoriasis.
- 3) To compare frequency of relapse between subjects who achieve a score of 0 (clear) on IGA (Investigator's Global Assessment) and subjects who do not achieve a score of 0 (clear) on IGA, within each group (Group 1 (6 months secukinumab) and Group 2 (3 months Placebo + 3 months secukinumab)).
- 4) To compare frequency of relapse between subjects who achieve a score of 0 (clear) on IGA between group 1 and group 2 (Group 1 (6 months secukinumab) and Group 2 (3 months Placebo + 3 months secukinumab)).
- 5) To evaluate the safety of secukinumab for the treatment of subjects with mild plaque-type psoriasis comparing the secukinumab-receiving mild psoriasis subjects (Group 1) and the placebo-receiving mild psoriasis subjects (Group 2) for 3 months.

12.7 * Primary Outcome(s)

Indicate which *variable(s)* will be assessed to judge the primary specific aim. Give measurement units, if applicable.

- 1) The proportion of subjects who have a reduction of 75% or more from baseline in the psoriasis area-and-severity index score (PASI 75) at week 12 (*primary endpoint*)¹
- 2) The proportion of subjects who have a reduction of 90% or more from baseline in the psoriasis area-and-severity index score (PASI 90) at week 12²
- 3) The proportion of subjects who achieve a score of 0 (clear) on a 5-point modified investigator's global assessment (IGA) at week 12³

1,2,3The 3 co-primary endpoints are subject to a step-down hierarchical closed testing procedure. (Primary objective is achieved if any null hypothesis is rejected following the order: PASI75, PASI90, IGA0).

12.8 * Secondary Outcome(s)

Indicate which *additional variable(s)* will be assessed to judge the secondary outcome(s). Give measurement units, if applicable.

- 1) The proportion of subjects who experience a psoriasis relapse at any time between week 24 and week 72. Psoriasis relapse is defined as loss of > 50% of the initial PASI improvement measured at week 24.
- 2) Severity of the relapses over the observation period.
- 3) Extent of relapse over the observation period.

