Langley et al. (2014) presented the results of two Phase 3 trials for Secukinumab: ERASURE and FIXTURE. Among others outcomes Langley reported the proportion of subjects with moderate or severe Psoriasis who achieve PASI75 (PASI score improvement over 75%) after 12 weeks of treatment in the 2 cohorts treated with Secukinumab 300 mg and the 2 Placebo cohorts with 245, 323, 246 and 324 subjects respectively. The worst scenario observed on Langley's results is: largest Placebo proportion=0.05 and smallest Secukinumab proportion=0.77. Assuming Langley's results as preliminary data, to find significant differences between groups by using a one-tail Fisher exact test with power equal to 0.95 and 99.9% of significance level, a sample size of 19 patients at each group (N=38) will be required. Considering the 5.6 % of dropout reported by Langley will be necessary to recruit 20 patients for each group (N=40). Power analysis for 3 co-primary endpoints and 19:19 patients is reported in the following table:

ENDPOINT	TREATMENT OBSERVED PROPORTION *	PLACEBO OBSERVED PROPORTION *	OBSERVED EFFECT SIZE*	SIGNIFICANCE LEVEL	POWER	DETECTABLE EFFECT SIZE
PASI 75	0.77	0.05	0.72	0.05	0.8	0.49
				0.05	0.9	0.55
				0.05	0.95	0.60
				0.01	0.8	0.42
				0.01	0.9	0.48
PASI 90	0.54	0.02	0.52	0.05	0.8	0.4
				0.05	0.9	0.47
				0.05	0.95	0.52
				0.01	0.8	0.52
				0.01	0.9	0.59
IGA0	0.24	0.01	0.23	0.05	0.8	0.37
				0.05	0.9	0.44
				0.05	0.95	0.50
				0.01	0.8	0.50
				0.01	0.9	0.56
				0.01	0.95	0.61

OR

ENDPOINT	TREATMENT OBSERVED PROPORTION *	PLACEBO OBSERVED PROPORTION *	OBSERVED EFFECT SIZE*	SIGNIFICANCE LEVEL	ESTIMATED POWER TO DETECT OBSERVED EFFECT SIZE
PASI 75	0.77	0.05	0.72	0.05	0.99
				0.01	0.99

PASI 90	0.54	0.02	0.52	0.05	0.99
				0.01	0.94
IGA 0	0.24	0.1	0.14	0.05	0.46
				0.01	0.25

* Langley et al. (2014)

2. Power Analysis for Exploratory Objectives/First outcome

Assuming the proportion of 300 mg secukinumab patients who achieve PASI 100 at week 24 as reported by Langley (0.4), the allocation ratio of subjects who achieve PASI 100 and subjects who not achieve PASI 100 for Group 1 (6 month of Secukinumab) will be 8:11. On that case a Fisher exact test to compare the proportion of patients who experience relapse with power equal to 0.80 and 95% of significance level will be able to detect significant differences only if the following relationship between proportions is observed:

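### The two power tables for the co-primary endpoints contradict each other and themselves: IGA 0 placebo rate 0.01 or 0.1, PASI 75 effects that shrink at the stricter alpha, and two powers for one PASI 90 effect

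*Combined protocol and SAP*

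**What the plan says.** Section 12.11, item 1, bases the sample size on PASI 75, with "largest Placebo proportion=0.05 and smallest Secukinumab proportion=0.77" taken from two published phase 3 trials, "by using a one-tail Fisher exact test with power equal to 0.95 and 99.9% of significance level". This gives 19 per arm. The text then says "Power analysis for 3 co-primary endpoints and 19:19 patients is reported in the following table". Two tables follow, joined by the word OR and both credited to the same publication.

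- The first lists detectable effects by alpha and power. Its IGA 0 block begins "IGA0 0.24 0.01 0.23 0.05 0.8 0.37", that is, treatment 0.24, placebo 0.01, effect 0.23. Its PASI 75 block begins "PASI 75 0.77 0.05 0.72 0.05 0.8 0.49".
- The second lists the power to detect the observed effect. Its IGA 0 block begins "IGA 0 0.24 0.1 0.14 0.05 0.46", that is, treatment 0.24, placebo 0.1, effect 0.14, power 0.46. The next row gives 0.25 at alpha 0.01.

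The first aim in section 12.6 is "To evaluate the efficacy of secukinumab for the complete resolution of mild plaque-type psoriasis after 3 months of secukinumab treatment". Section 12.7 tests the three endpoints in sequence: "Primary objective is achieved if any null hypothesis is rejected following the order: PASI75, PASI90, IGA0". Section 12.10 names Fisher's exact test for all comparisons of proportions.

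**The concern.** Three things in these tables do not fit together.

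1. IGA 0 has two placebo rates that differ tenfold, and the power printed beside 0.1 is not the power for 0.1.
2. For PASI 75 the detectable effect gets smaller when alpha is tightened at fixed sample size and power. PASI 90 and IGA 0 in the same table move the right way.
3. For PASI 90 the two tables give different powers for the same effect, the same rates and the same 19 per arm.

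The first matters most. The leading aim is complete resolution, and IGA 0 is the only clear-skin endpoint in the primary sequence (PASI 100 at week 12 is secondary, section 12.8). Someone interpreting a non-significant IGA 0 result needs to know what chance the trial had of finding the assumed difference.

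**Working it through.** **Inputs.** 19 per arm; rates as printed in section 12.11; Fisher's exact test (sections 12.10 and 12.11). One-sided is the basis stated for the sample size; two-sided is shown for comparison. Power is the sum, over all 20 × 20 possible outcomes, of the product of the two binomial probabilities wherever Fisher's p is at or below alpha.

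**The plan's own sample size.** Reading the 99.9% level as one-sided alpha 0.001, 0.77 versus 0.05 gives power 0.943 with 18 per arm and 0.964 with 19. The stated 19 per arm reproduces.

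**Second table, PASI 75 and PASI 90.** One-sided power at alpha 0.05 / 0.01 is above 0.99 / above 0.99 for PASI 75 (printed 0.99 / 0.99) and 0.988 / 0.943 for PASI 90 (printed 0.99 / 0.94). These rows reproduce, so the second table uses one-sided Fisher.

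**IGA 0, by hand.** With no clear placebo patients, 4 clear treated patients give p = C(19,4)/C(38,4) = 3876/73815 = 0.0525, which fails at 0.05; 5 give C(19,5)/C(38,5) = 11628/501942 = 0.023. So 5 are needed against 0 on placebo. In the same way, 6 are needed against 1 and 8 against 2. With treatment rate 0.24, the chance of at least 5, 6 or 8 of 19 is 0.4936, 0.2950 or 0.0629.

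- Placebo 0.01: the chance of 0, 1 or 2 clear on placebo is 0.8262, 0.1586 or 0.0144. Power = 0.8262×0.4936 + 0.1586×0.2950 + 0.0144×0.0629 = 0.4078 + 0.0468 + 0.0009 = 0.4555.
- Placebo 0.10: the same chances are 0.1351, 0.2852 and 0.2852. Power = 0.0667 + 0.0841 + 0.0179, plus 0.0045 from 3 or more on placebo, = 0.173.

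| IGA 0 rates | One-sided, alpha 0.05 / 0.01 | Two-sided, alpha 0.05 / 0.01 | Printed |
|---|---|---|---|
| 0.24 v 0.01 | 0.456 / 0.254 | 0.43 / 0.13 | – |
| 0.24 v 0.10 | 0.173 / 0.060 | 0.12 / 0.03 | 0.46 / 0.25 |

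The printed powers therefore belong to 0.01. Among normal-approximation alternatives, the most favourable at 0.24 v 0.10 (one-sided arcsine) reaches only 0.318 / 0.124.

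**PASI 75, first table.** Every outcome that rejects at alpha 0.01 also rejects at 0.05. At fixed sample size and power, the detectable effect therefore cannot fall as alpha is tightened, whatever the test. Exact power of the printed effects (placebo 0.05):

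| Effect, alpha | Printed power | One-sided | Two-sided |
|---|---|---|---|
| 0.49, 0.05 | 0.80 | 0.96 | 0.92 |
| 0.42, 0.01 | 0.80 | 0.72 | 0.59 |
| 0.48, 0.01 | 0.90 | 0.84 | 0.74 |

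**PASI 90, effect 0.52 (0.54 v 0.02).**

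| Source | Alpha 0.05 | Alpha 0.01 |
|---|---|---|
| First table | 0.95 | 0.80 |
| Second table | 0.99 | 0.94 |
| Fisher, one-sided | 0.988 | 0.943 |
| Fisher, two-sided | 0.974 | 0.886 |

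The second table agrees with one-sided Fisher. The first agrees with neither form.

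**The case against.** The best defence is that these are presentation slips with innocent causes.

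- The 0.1 looks like a misprint for 0.01, in which case 0.46 and 0.25 are correct.
- The PASI 75 alpha labels look swapped. After a swap the printed effects come within 0.026 of two-sided Fisher, and one-sided power would be understated rather than overstated (0.42 at alpha 0.05 has about 0.90 against 0.80 printed).
- The first table's PASI 90 figures are close to a two-sided continuity-corrected z-test (0.937 and 0.781 at effect 0.52), so the tables may simply use different methods.
- IGA 0 is last in the sequence and does not govern primary success. Its low power is already visible, the assumed PASI 75 effect of 0.72 exceeds every detectable effect in either version, and recruitment is closed.

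Much of this stands as explanation, and it limits the weight of the point. The direction of the PASI 75 error does depend on whether the labels or the effects are wrong. But a likely cause does not make the printed cells right. The 0.1 is carried into the effect (0.24 − 0.1 = 0.14), so it is not damage from reading the PDF. The swap reproduces the PASI 75 values only approximately, and the plan names no z-test. The word OR offers the tables as alternatives, yet they disagree.

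**Conclusion.** The concern holds and should be fixed. The stated IGA 0 power is wrong for the rates printed beside it: 0.17 and 0.06 rather than 0.46 and 0.25 (one-sided, alpha 0.05 and 0.01). It is right if the placebo rate is 0.01. That is the likelier value, because the same tables put placebo PASI 75 at 0.05 and PASI 90 at 0.02, but only the source can settle it. IGA 0 power is below 50% either way. As labelled, the PASI 75 rows at alpha 0.01 overstate power (0.72 and 0.84 one-sided, against 0.80 and 0.90). The two PASI 90 statements are not on one basis.

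These figures assume 19 evaluable patients per arm and the printed rates, and they are powers for each endpoint taken alone. Requiring the two earlier rejections costs IGA 0 at most (1 − 0.9998) + (1 − 0.9876) = 0.0126 at one-sided 0.05. The sample size and the PASI 75 step are unaffected. The alpha 0.01 / power 0.95 rows absent for PASI 75 and PASI 90 may have been lost in reading the PDF and are not counted as an error.

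**What to change.** 1. Check the IGA 0 placebo rate against the cited publication and use one value in both tables. If it is 0.01, change 0.1 to 0.01 and 0.14 to 0.23 in the second table; its one-sided powers then stand. If it is 0.10, the powers become 0.17 and 0.06, and the first table's IGA 0 rows change as well.
2. State one alpha level and sidedness, the same as the testing sequence will use, and recompute both tables with Fisher's exact test. Detectable effects at power 0.80 / 0.90 / 0.95 with 19 per arm (correct to about 0.01):

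| Endpoint (placebo rate) | One-sided 0.05 | One-sided 0.01 | Two-sided 0.05 | Two-sided 0.01 |
|---|---|---|---|---|
| PASI 75 (0.05) | 0.36 / 0.42 / 0.48 | 0.46 / 0.53 / 0.58 | 0.41 / 0.47 / 0.53 | 0.51 / 0.58 / 0.63 |
| PASI 90 (0.02) | 0.34 / 0.39 / 0.44 | 0.42 / 0.48 / 0.53 | 0.36 / 0.42 / 0.48 | 0.47 / 0.53 / 0.58 |
| IGA 0 (0.01) | 0.33 / 0.38 / 0.43 | 0.40 / 0.46 / 0.50 | 0.35 / 0.40 / 0.45 | 0.45 / 0.51 / 0.56 |
| IGA 0 (0.10) | 0.39 / 0.46 / 0.51 | 0.50 / 0.57 / 0.63 | 0.44 / 0.51 / 0.56 | 0.55 / 0.60 / 0.65 |

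3. For the second table, power at alpha 0.05 is above 0.99 for PASI 75, 0.99 for PASI 90 and 0.46 for IGA 0 (0.17 if the rate is 0.10) one-sided. Two-sided it is above 0.99, 0.97 and 0.43 (0.12).
4. Say in the text that IGA 0 has below 50% power on either rate.

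The cost is corrected cells, a sentence naming the level and sidedness, and the statement on IGA 0 power. Sample size, design and testing order do not change.

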2	baseline	baseline	Secukinumab 300 mg	Placebo	Skin biopsy & blood

3		week 1	Secukinumab 300 mg	Placebo	
4		week 2	Secukinumab 300 mg	Placebo	
5		week 3	Secukinumab 300 mg	Placebo	
6	month 1	week 4	Secukinumab 300 mg	Placebo	
7	month 2	week 8	Secukinumab 300 mg	Placebo	
8	month 3	week 12	check primary endpoint (IGA 0,1 at week 12)		Skin biopsy & blood
			Secukinumab 300 mg	Secukinumab 300 mg	
9		week 13	Placebo	Secukinumab 300 mg	
10		week 14	Placebo	Secukinumab 300 mg	
11		week 15	Placebo	Secukinumab 300 mg	
12	month 4	week 16	Secukinumab 300 mg	Secukinumab 300 mg	
13	month 5	week 20	Secukinumab 300 mg	Secukinumab 300 mg	
14	month 6	week 24	Secukinumab 300 mg	Secukinumab 300 mg	Skin biopsy & blood
15	month 9	week 36			
16	month 12	week 48	observation	observation	
17	month 15	week 60			
18	month 18	week 72	check secondary endpoint (recurrence)		Skin biopsy & blood
	*Optional skin biopsy and blood : when recurrence occurs after week 24				

Study Visits

Visit 1--Screening Visit/Enrollment

- Vital signs (weight, height, blood pressure, temperature, heart rate, respiration)
- Physical exam and questions your general health
- Serum pregnancy if female of child-bearing potential
- POCT HIV
- Blood for Hepatitis B (antibody as well antigen) and C, Comprehensive metabolic panel, Lipid panel, Hgb A1c, CBC and optional QuantFERON-TB Gold (only if no PPD screen)
- Assessment of psoriasis status using several scales: Investigator Global Assessment (IGA), Psoriasis Area and Severity Index (PASI) with BSA, Dermatology Life Quality Index (DLQI), PASE
- PPD / TB skin test or QuantIFERON-TB Gold

Visit 1.1--PPD Reading Visit

- If PPD was placed at Screening Visit, PPD reading 48 hours later
- Chest X-Ray. (If PPD Positive)

Visit 2--Baseline visit (and first dose)

- Medications history
- Physical exam (symptom driven as indicated)
- Vital signs (weight, body temperature, heart rate and blood pressure)
- POCT Pregnancy
- Fasting Blood PAX DNA/RNA, CBC, SST (serum storage) sample, Comprehensive Metabolic Panel, Lipid panel, and Hgb A1c.
- Two 6mm skin biopsies, 1 lesional, 1 non-lesional.
- Medical photography
- Assessment of psoriasis, PGA, PASI with BSA, PASE, DLQI
- Adverse event assessment
- Dose of Secukinumab or placebo by subcutaneous injection.
- Observation period of 15 minutes (+/- 5 minutes) post study drug administration
- Subject will be offered a meal at end of visit.

Visit 3 to 7 and 9 to 13 --(Week 1 to 8 and 13 to 20)

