Proportion of patients from Group 1, who achieve PASI 100 at week 24 and experience relapse	Proportion of patients from Group 1, who not achieve PASI 100 at week 24 and experience relapse
0.00	0.45
0.13	0.73
0.25	0.82
0.38	0.91
0.50	1.00

Assuming the proportion of 300 mg secukinumab patients who achieve PASI 100 at week 12 as reported by Langley (0.3), the allocation ratio of subjects who achieve PASI 100 and subjects who not achieve PASI 100 for Group 1 (6 month of Secukinumab) will be 6:13. On that case a Fisher exact test to compare the proportion of patients who experience relapse with power equal to 0.80 and 95% of significance level will be able to detect significant differences only if the following relationship between proportions is observed:

Proportion of patients from Group 2, who achieve PASI 100 at week 24 and experience relapse	Proportion of patients from Group 2, who not achieve PASI 100 at week 24 and experience relapse
0.00	0.54
0.17	0.77
0.33	0.85
0.50	1.00

With the previous assumptions, the allocation ratio of subjects who achieve PASI 100 in Groups 1 and 2 will be 8:6. On that case a Fisher exact test to compare the proportion of patients who experience relapse with power equal to 0.80 and 95% of significance level will be able to detect significant differences only if the following relationship between proportions is observed:

Proportion of patients from Group 1 who achieve PASI 100 at week 24 and experience relapse	Proportion of patients from Group 2 who achieve PASI 100 at week 24 and experience relapse
0.00	0.67
0.13	0.83
0.25	1.00

3. Power Analysis for Exploratory Objective/Second outcome

To compare the time to relapse between groups with a sample size of 19:19 a Wilcoxon-Mann-Whitney test for nonrelated samples with power equal to 0.8 and 95% of significance level will be able to detect differences only if the effect size observed is equal or larger than 0.96

12.12 * Will samples be coded?

Yes No

If Yes, Please describe coding scheme consistent with GCP. If samples will not be coded, please provide justification for this proposed departure from GCP practice.

Samples will be coded using GCP with the following sequence

NSK__-001. NSK__-002, etc.

If available, upload the Data and Sample Sharing Management Plan approved by RU IT.

Version	Title	Category	Expiration Date	Document Outcome	Checked Out	View Document
No Document(s) have been attached to this form.						

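### Aims 3 and 4 classify patients by IGA 0 at no stated visit, but the power tables in 12.11 item 2 are built on PASI 100 at week 24

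*Combined protocol and SAP*

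**What the plan says.** **Aims (12.6).** Aim 3 compares relapse between patients who reach IGA 0 and "subjects who do not achieve a score of 0 (clear) on IGA, within each group". Aim 4 is "To compare frequency of relapse between subjects who achieve a score of 0 (clear) on IGA between group 1 and group 2". Neither names a visit.

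**Outcomes (12.7, 12.8).** IGA 0 is defined as an outcome once, as item 3 of 12.7: "The proportion of subjects who achieve a score of 0 (clear) on a 5-point modified" investigator's global assessment, at week 12. No secondary outcome uses IGA. Relapse is counted from week 24 to week 72, relative to the PASI improvement measured at week 24.

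**Power (12.11 item 2).** The clear and not-clear groups are defined by PASI 100. For Group 1: "subjects who achieve PASI 100 and subjects who not achieve PASI 100 for Group 1 (6 month of Secukinumab) will be 8:11", from a week-24 rate of 0.4. A second split, from a week-12 rate of 0.3, is described as "for Group 1 (6 month of Secukinumab) will be 6:13", but its table is headed "Proportion of patients from Group 2, who achieve PASI 100 at week 24 and experience relapse". The between-group comparison then uses 8:6. All three tables are headed week 24.

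**Treatment and visits (12.6, 12.9).** The sequence for the second arm is "Group 2 : 3 months placebo + 3 months secukinumab + 12 months observation". The visit table has "check primary endpoint (IGA 0,1 at week 12". The visit list for weeks 12 and 24 names PGA and PASI; the visit lists name IGA only at screening.

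**The concern.** The aims use one scale and their power calculation uses another. Nothing in the plan says that PASI 100 stands in for IGA 0. The documents' own rates on drug at week 12 are 0.24 for IGA 0 and 0.3 for PASI 100.

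The missing visit matters as well. Someone looking in the plan for a definition of IGA 0 finds only week 12, before Group 2 has received any secukinumab. Relapse after stopping drug is the trial's stated purpose, and Aims 3 and 4 ask whether clearance predicts it. With about 19 patients per group, moving a few patients between cells can change a Fisher test. A classifier left open on scale and visit could be settled after relapse results are known.

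**Working it through.** **Inputs, all from 12.11 unless noted.** n = 19 per group. PASI 100 on drug: 0.4 at week 24 and 0.3 at week 12. IGA 0 on drug: 0.24 at week 12 (12.7 places this outcome there). IGA 0 on placebo: 0.01 in the first power table and 0.1 in the second. Fisher's exact test, power 0.80, alpha 0.05 (written as a 95% significance level). Sidedness is not stated for these comparisons; two-sided is assumed here.

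**1. Reproduce the printed splits.**
- 19 × 0.4 = 7.6, so 8:11, as printed.
- 19 × 0.3 = 5.7, so 6:13, as printed.
- Clear patients in Group 1 against Group 2: 8:6, as printed.

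The splits are therefore PASI 100 splits. Group 1 cannot be both 8:11 and 6:13. The second uses the rate after three months, which fits Group 2's exposure and the table's own heading, so the label in the text is a slip.

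**2. Put IGA 0 in its place.** The only IGA 0 rate on drug is 0.24 at week 12: 19 × 0.24 = 4.56, so 5:14. The documents give no week-24 IGA 0 rate, so the Group 1 split after six months, and hence the Aim 4 split, cannot be computed for IGA 0 without an assumption.

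**3. The week-12 reading for Group 2 (placebo only).**
- At 0.01: expected clear = 19 × 0.01 = 0.19; chance of none = 0.99^19 = 0.826.
- At 0.1: expected clear = 19 × 0.1 = 1.9; chance of none = 0.9^19 = 0.135.

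On either figure, Aim 4 and the Group 2 part of Aim 3 would rest on about 0 to 2 clear patients.

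**4. What the detectable differences represent.** Take the row with no relapse among clear patients. The smallest second count with two-sided p ≤ 0.05, its exact power if those proportions are the true ones, and the true proportion that gives 80% exact power are:

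| Split | Smallest significant pair | p | Exact power at that pair | True proportion for 80% power |
|---|---|---|---|---|
| 8:11 | 0/8 v 5/11 (0.45, printed) | 0.0445 | 0.615 | about 0.54 |
| 6:13 | 0/6 v 7/13 (0.54, printed) | 0.0436 | 0.611 | about 0.62 |
| 5:14 | 0/5 v 8/14 (0.57) | 0.0445 | 0.611 | about 0.65 |

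The printed rows are the smallest observed differences that reach significance. Across all printed rows, exact two-sided power is 0.57 to 0.70, except 0.25 v 1.00 at 8:6, where it is 0.89. Replacing the variable while keeping this method would again not give the stated 0.80.

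**The case against.** The best defence is that the context points to week 24. The aims name the groups by their full regimens, relapse is counted from week 24, and every table in 12.11 item 2 is headed week 24. Week 12 belongs to the outcome that serves Aim 1. This largely stands: week 24 is the likely intention, although the plan never says so for IGA.

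It also stands that the objectives are labelled exploratory, that the 40 patients are justified by PASI 75, and that the table below 6:13 already shows the right group. The numerical shift is small for Group 2: one patient, and 0.62 to 0.65 for 80% power. The contrast of 0.24 with 0.3 is weak evidence about the scales, since 0.3 is given to one decimal with no cohort named.

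A reader might infer three stronger things that the documents do not support:
- That Aim 4 and half of Aim 3 will have no data. This needs the week-12 reading, and the 83% chance of no clear patient uses only one of the two printed placebo rates.
- That reaching IGA 0 at any time would count, so that staying relapse-free helps a patient enter the clear group. Nothing suggests that clear status is assigned during follow-up.
- That Aim 4 shrinks to 8:5. That figure takes the 8 from PASI 100 and the 5 from IGA 0.

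None of this removes the mismatch of scale or supplies the missing visit.

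**Conclusion.** The point holds as an inconsistency to correct. Aims 3 and 4 use IGA 0 at an unstated visit; their only power calculation uses PASI 100 at week 24 and gives Group 1 two different splits. The printed splits and detectable differences therefore do not belong to the variable in the aims.

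If week 24 is meant, the numerical effect is modest where it can be computed at all: with no relapse in clear patients, the relapse proportion needed in the others for 80% power is about 0.54 at 8:11, 0.62 at 6:13 and 0.65 at 5:14. If the only defined IGA 0 visit were used, Group 2 would have an expected 0.19 to 1.9 clear patients and the comparisons would be close to unworkable. That is the outer bound of the ambiguity rather than the expected outcome.

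These figures assume 19 patients per group, two-sided tests and the rates printed in 12.11. The total sample size and the primary comparison are unaffected.

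**What to change.** 1. Define clear status once for Aims 3 and 4, scored at the week-24 visit in both groups and fixed before relapse follow-up begins. There are two ways:
   - Change both aims to PASI 100 at week 24. PASI is already listed at that visit and 12.11 already uses it. This is the simpler route.
   - Keep IGA 0 at week 24, after reconciling IGA with the PGA named in the week-24 visit list and stating which global scale is scored.
2. Change the Group 1 label on 6:13 to Group 2.
3. Recompute the three tables in 12.11 item 2 for the chosen variable. If IGA 0 is kept, show an assumed range of clear rates, for example 0.24 to 0.40, because no week-24 rate is given. Report true proportions that give 80% exact power and state the sidedness. Otherwise, relabel the rows as the smallest observed significant differences.
4. Reconcile the two placebo IGA 0 rates, 0.01 and 0.1.

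The cost is protocol wording and three recalculated tables. The PASI 100 route needs no new data; the IGA 0 route needs none if the scale scored at week 24 proves to be IGA. The stated figures for these exploratory aims will look slightly less favourable.
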